**Table 13. Enthesial Sites Examined for SPARCC Calculation (Left and Right)**

Medial epicondyle	Lateral epicondyle	Supraspinatus insertion into greater tuberosity of humerus	Greater trochanter
Quadriceps insertion into superior border of patella	Patellar ligament insertion into inferior pole of patella or tibial tubercle	Achilles tendon insertion into calcaneum	Plantar fascia insertion into calcaneum

**Presence of Enthesitis Based on SPARCC:**

If enthesitis is present with any of the 16 sites for SPARCC, the subject is counted as a subject with enthesitis based on SPARCC.

#### **10.7.18 Functional Assessment of Chronic Illness Therapy-Fatigue (FACIT-Fatigue)**

The FACIT-Fatigue is a 13-item questionnaire that assesses self-reported fatigue and its impact upon daily activities and function.

The purpose of FACIT-Fatigue in this study is to assess the impact of fatigue on subjects with PsA.

Number of items: 13 items: I feel fatigued (-), I feel weak all over (-), I feel listless (washed out) (-), I feel tired (-), I have trouble starting things because I am tired (-), I have trouble finishing things because I am tired (-), I have energy (+), I am able to do my usual activities (+), I need to sleep during the day (-), I am too tired to eat (-), I need help doing my usual activities (-), I am frustrated by being too tired to do the things I want to do (-), I have to limit my social activity because I am tired (-).

Response options/scale: Answers are based on a 5-point Likert scale. Responses of "not at all," "a little," "somewhat," "quite a bit," and "very much" are available for each question, and correspond to scores of 0, 1, 2, 3, and 4, respectively (4 = not at all fatigued

to 0 = very much fatigued). The FACIT Fatigue Scale is ranged from 0 to 52 and the higher the score, the better the quality of life.

Score for each item is calculated by either subtracted from 4 or adding 0 depending on whether it is a reversal item or not. FACIT Fatigue Scale is then calculated by adding up all item scores, multiplied by 13 and divided by the number of items answered. It is essentially a prorated subscale if there are missing values for some items. If less than or equal to 50% of the items are answered (e.g., 6 out of 13), the proration is not acceptable and the scale will not be computed.

Recall period for items: 7 days.

#### **10.7.19                    Bath Ankylosing Spondylitis Disease Activity Index (BASDAI)**

The BASDAI is composed of 6 questions investigating 5 domains (fatigue, spinal pain, joint pain/swelling, areas of localized tenderness, morning stiffness), with 1 item for each of the first four domains and 2 items for the last domain (morning stiffness). Each item is scored on a one through 10 scale. A lower score indicates less disease activity.

Scoring of the BASDAI is as follows:

1. Measure each item of the BASDAI in centimeters (out of a total of 10)
2. BASDAI Score =  $0.2 * (Question\ 1 + Question\ 2 + Question\ 3 + Question\ 4 + 0.5 * Question\ 5 + 0.5 * Question\ 6)$

The BASDAI Score ranges from 0 – 10. If one or more items are unanswered, take the average of the non-missing items. If there is more than one mark for an item, take the average.

Below are the 6 questions.

3. How would you describe the overall level of fatigue/tiredness you have experienced?
4. How would you describe the overall level of AS neck, back or hip pain you have had?
5. How would you describe the overall level of pain/swelling in joints other than neck, back or hips you have had?
6. How would you describe the overall level of discomfort you have had from any areas tender to touch or pressure?
7. How would you describe the overall level of morning stiffness you have had from the time you wake up?
8. How long does your morning stiffness last from the time you wake up?

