The SF-36 is a widely used and extensively studied instrument to measure health-related quality of life among healthy subjects and patients with acute and chronic conditions. It consists of eight subscales that can be scored individually: Physical Functioning, Role-Physical, Bodily Pain, General Health, Vitality, Social Functioning, Role-Emotional, and Mental Health.⁴ Two overall summary scores, the Physical Component Summary (PCS) and the Mental Component Summary (MCS) also can be computed.¹ The SF-36 has proven useful in monitoring general and specific populations, comparing the relative burden of different disease, differentiating the health benefits produced by different treatments, and in screening individual subjects.

The purpose of the SF-36 in this study is to assess the Health Related Quality of Life (HRQoL) of subjects. Given the acute nature of this disease, version 2, with a 1-week recall period, will be used in this study.

Functional Assessment of Chronic Illness Therapy-Fatigue (FACIT-F)^{7,8,34}

The FACIT-F is a 13-item questionnaire that assesses self-reported fatigue and its impact upon daily activities and function.

The purpose of FACIT-F in this study is to assess the impact of fatigue on subjects with PsA.

Number of items: 13 items.

Response options/scale: Answers are based on a 5-point Likert scale. Responses of "not at all," "a little," "somewhat," "quite a bit," and "very much" are available for each question, and correspond to scores of 0, 1, 2, 3, and 4, respectively.

Recall period for items: 7 days.

BASDAI (Bath Ankylosing Spondylitis Disease Activity Index)³³

Each question is answered on a 0 to 10 scale. For Questions 1 – 5, 0 means none and 10 means very severe; for Question 6, 0 means 0 hours and 10 means 2 or more hours. All questions refer to last week.

1. How would you describe the overall level of fatigue/tiredness you have experienced?
2. How would you describe the overall level of AS neck, back or hip pain you have had?
3. How would you describe the overall level of pain/swelling in joints other than neck, back or hips you have had?
4. How would you describe the overall level of discomfort you have had from any areas tender to touch or pressure?
5. How would you describe the overall level of morning stiffness you have had from the time you wake up?
6. How long does your morning stiffness last from the time you wake up?

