Calculation of BASDAI: compute the mean of Questions 5 and 6. Calculate the sum of the values of Questions 1 – 4 and add the result to the mean of Questions 5 and 6. Divide the result by 5.

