## 6.5 Missing Data Handling

All data will be summarized as observed, and thus a subject who does not have an evaluation on a scheduled visit will be excluded from the summary for that visit.

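### The SAP scores an incomplete BASDAI as a plain item average with no minimum, which over-weights morning stiffness when some of Questions 1–4 are skipped

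*SAP*

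**What the plan says.** SAP 10.7.19 describes six questions covering five domains, with two of the questions on morning stiffness. Its complete-data score is 0.2 × (Q1 + Q2 + Q3 + Q4 + 0.5 × Q5 + 0.5 × Q6), and it states that "The BASDAI Score ranges from 0 – 10". Protocol Appendix R gives the same score in steps: "compute the mean of Questions 5 and 6", then "Calculate the sum of the values of Questions 1 – 4 and add the result to the mean of Questions 5 and 6", then divide by 5.

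For incomplete forms, SAP 10.7.19 says: "If one or more items are unanswered, take the average of the non-missing items". It mentions no weights, no domain step and no minimum. The protocol has no missing-item rule for BASDAI. The general rule in SAP 6.5 is "All data will be summarized as observed, and thus a subject who does not have an evaluation on a scheduled visit will be excluded" from that visit's summary. This covers absent evaluations, not partly completed ones.

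Three other scores in the same SAP do have a floor:

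- FACIT-Fatigue (SAP 10.7.18): "If less than or equal to 50% of the items are answered (e.g., 6 out of 13), the proration is not acceptable".
- HAQ-DI (SAP 10.7.7): six of eight categories are required, and category scores are averaged rather than raw items.
- mNAPSI (SAP 10.7.10): prorated by weight, and set to missing if more than half of the weight is absent.

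**The concern.** The complete-data formula counts stiffness as one domain out of five. The missing-item sentence treats every answered question alike, so the two stiffness questions count as two domains. If a subject completes the form at baseline and skips one of Questions 1–4 later, part of the recorded change comes from the change of weights.

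With no floor, a form with one answered question also yields a BASDAI score, and that score enters the mean change and its 95% CI with the same standing as a complete one. Skipped items are plausible because Protocol 10.2 has patient-reported outcomes completed on paper, and the SAP sentence itself anticipates them.

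**Working it through.** **Inputs.** The item weights come from the SAP 10.7.19 formula: 0.2 for each of Q1–Q4 and 0.1 for each of Q5 and Q6. Items are taken as 0 to 10, following Protocol Appendix R ("Each question is answered on a 0 to 10 scale"). SAP 10.7.19 describes the items as running from one to 10, which does not fit its own 0–10 score range. Write S = (Q5 + Q6)/2.

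**Reproducing the plan's figure.** All items at 0 gives 0.2 × 0 = 0. All items at 10 gives 0.2 × (40 + 5 + 5) = 10. The stated range is reproduced, and the SAP and protocol forms are algebraically the same.

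**One of Q1–Q4 missing (say Q1), both stiffness items answered.**

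- SAP rule: (Q2 + Q3 + Q4 + Q5 + Q6)/5. Stiffness weighs 2/5 = 0.40.
- Complete formula: stiffness weighs 0.1 + 0.1 = 0.20.
- Average of the four available domains: (Q2 + Q3 + Q4 + S)/4. Stiffness weighs 0.25.

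Because Q5 + Q6 = 2S, the SAP rule equals 0.2 × (S + Q2 + Q3 + Q4 + S). It is the complete formula with the missing domain filled by the stiffness mean alone.

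**Examples with Q1 skipped.**

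| Item values | Complete | SAP rule | Domain average |
|---|---|---|---|
| Q1–Q4 = 3, Q5 = Q6 = 7 | 0.2 × (12 + 7) = 3.8 | (9 + 14)/5 = 4.6 | (9 + 7)/4 = 4.0 |
| Q1–Q4 = 6, Q5 = Q6 = 2 | 0.2 × (24 + 2) = 5.2 | (18 + 4)/5 = 4.4 | (18 + 2)/4 = 5.0 |

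In these two examples a stable subject shows an apparent change of +0.8 or −0.8 under the SAP rule, and +0.2 or −0.2 under domain averaging. The direction depends on whether stiffness is higher or lower than the other domains.

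**Largest gap between the two rules.** The gap is the excess stiffness weight multiplied by the difference between S and the mean of the answered Q1–Q4. That difference is at most 10.

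| Q1–Q4 missing | Stiffness weight, SAP | Stiffness weight, domain | Largest gap |
|---|---|---|---|
| 1 | 2/5 = 0.40 | 1/4 = 0.25 | 0.15 × 10 = 1.5 |
| 2 | 2/4 = 0.50 | 1/3 = 0.33 | 1/6 × 10 = 1.67 |
| 3 | 2/3 = 0.67 | 1/2 = 0.50 | 1/6 × 10 = 1.67 |

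**Where the rules agree.** If only Q5 or only Q6 is missing, five items remain, one per domain, and each domain weighs 1/5 = 0.20 as in the complete score. If both are missing, Q1–Q4 stay equally weighted under either rule. There are 2^6 − 2 = 62 patterns with one to five items answered. The rules differ in 4 + 6 + 4 = 14 of them: both stiffness items answered, and one, two or three of Q1–Q4 missing. These are counts of patterns, not frequencies.

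**Single-item scores.** In the second example (complete score 5.2), a form with only Q1 answered scores 6 and a form with only Q6 answered scores 2.

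**The case against.** Several counter-arguments have force.

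- **Scope.** A reader might infer that any missing item breaks the weighting. It does not: the domain weights hold in 48 of the 62 patterns, including loss of Q5, Q6 or both.
- **Gap or error.** The 1.5 points might be taken as the largest possible error. It is a gap between two rules. Measured against the complete score with Q1 missing, the SAP rule errs by 0.2 × (S − Q1) and domain averaging by 0.2 × (mean of the four available domains − Q1). Either can reach 2.0.
- **Accuracy in a given case.** With Q2–Q4 = 3 and Q5 = Q6 = 7, the complete score is 0.2 × (Q1 + 16). The SAP's 4.6 is closer when Q1 exceeds 5.5, and 4.0 is closer when Q1 is below 5.5. So the SAP rule is not always worse. Even so, filling a missing domain from all available domains is easier to defend than filling it from stiffness alone.
- **Scale.** An incomplete score is not on a different scale. Both run 0–10, and domain averaging also moves the stiffness weight, from 0.20 to 0.25.
- **A milder reading.** The sentence could mean filling the missing item with the average of the answered items and then applying the formula. With one of Q1–Q4 missing, stiffness would weigh 0.2 + 0.2 × 0.4 = 0.28, and the gap from domain averaging would be at most 0.03 × 10 = 0.3. A single item would still give a score, and the possibility of two readings is itself a reason to clarify.
- **Consistency.** The SAP has no uniform floor. Joint counts, dactylitis count, LEI and SPARCC have none, so the comparison with FACIT-Fatigue, HAQ-DI and mNAPSI shows available conventions rather than a broken rule.

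**Conclusion.** The point stands in a limited form. Read plainly, the missing-item sentence departs from the five-domain weighting in the SAP's own formula and in Protocol Appendix R when both stiffness items are answered and some but not all of Questions 1–4 are missing. It also allows a score from one item.

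The size rests on the plain-average reading and on items scored 0–10.

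The priority is low. BASDAI change is listed among the further endpoints (SAP 10.4), is limited to subjects with inflammatory spondylitis at the Study 1311.5 baseline, and is summarized without testing. A reader might infer that the reported mean change will be biased. The documents do not support that: they give no rate of skipped items, so the effect on the mean cannot be computed, and the sign of the distortion varies between subjects.

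**What to change.** Replace the sentence in SAP 10.7.19 with a domain-level rule. Score stiffness as the mean of Questions 5 and 6, or as the one answered; average the available domain scores; and set BASDAI to missing below a stated minimum, for example 4 of 5 domains. The cut-off is the sponsor's choice and does not follow from the documents. At 4 of 5, forms missing two or three of Questions 1–4 would be set to missing rather than rescored. Averaging domains follows the HAQ-DI approach of averaging categories, and a floor follows HAQ-DI, FACIT-Fatigue and mNAPSI.

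The cost is one SAP sentence and its programming. The downside is that a few scores become missing in an already restricted subgroup.

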#### **10.7.20                    Modified Total Sharp Score (mTSS)**

The radiographic outcome will be assessed and scored according to Sharp's method (Van der Heijde modification) centrally by two qualified physicians/radiologists who will be blinded to the site number, subject number, treatment allocation, time sequence and clinical response.

##### **Calculation of the Modified Total Sharp Score**

To obtain the total mTSS score, scores for erosions and JSN in both the hands and feet will be added together.

The range of scores is summarized below.

	Hands	Feet	Total (Hands and Feet)
Erosion Score Range	0 - 200	0 - 120	0 - 320
Joint Space Narrowing Range	0 - 160	0 - 48	0 - 208
mTSS Range for Erosion and JSN	0 - 360	0 - 168	0 - 528

The following joints will be examined for assessing Erosions:

Foota	Handb			
1 st IP	1 st IP	3 rd MCP	5 th MCP	Ulnar
1 st MTP	1 st MCP	3 rd DIP	5 th DIP	MC1
2 nd MTP	2 nd PIP	4 th PIP	Multangular c	
3 rd MTP	2 nd MCP	4 th MCP	Navicular	
4 th MTP	2 nd DIP	4 th DIP	Lunate	
5 th MTP	3 rd PIP	5 th PIP	Radius	

- a. IP: Inter-Phalangeal, MTP: Metatarso-Phalangeal.
- b. IP: Inter-Phalangeal, PIP: Proximal Inter-Phalangeal, MCP: Metacarpophalangeal, DIP: Distal Inter-Phalangeal.
- c. Trapezium/Trapezoid as read as one unit-Multangular.

The following joints will be examined for assessing Joint Space Narrowing:

Foot a	Hand b			
1 st IP	1 st MCP	3 rd DIP	5 th DIP	RC
1 st MTP	2 nd PIP	4 th PIP	3 rd CMC	1 st IP
2 nd MTP	2 nd MCP	4 th MCP	4 th CMC	
3 rd MTP	2 nd DIP	4 th DIP	5 th CMC	
4 th MTP	3 rd PIP	5 th PIP	MN	
5 th MTP	3 rd MCP	5 th MCP	CNL	

a. IP: Inter-Phalangeal, MTP: Metatarso-Phalangeal.  
 b. PIP: Proximal Inter-Phalangeal, MCP: Metacarpo-Phalangeal, CMC: Carpo-Metcarpal, MN: Multangular-Navicular, CNL: Capitate-Navicular Lunate, RC: Radio-Carpal, DIP: Distal Inter-Phalangeal.

For each Joint and Bone assessed scores range as follows:

- Erosions: 0 – 5 (hands/wrists) or 0 – 10 (feet) to characterize the extent of erosions (where 0 denotes no erosion).
- Joint Space Narrowing: 0 – 4 to characterize the extent of Joint Space Narrowing (JSN) (where 0 denotes no narrowing).
- The categorical scores G and P could be possible for the entry for the following situation:
  - Osteolysis in the form of pencil-in-cup: Osteolysis of proximal phalanx and the base of the distal phalanx resulting in a pencil like proximal phalanx covered by cup like base of the distal phalanx. Pencil-in-cup will be scored as "P" where applicable.
  - Gross Osteolysis: Osteolysis of the phalanx resulting a loss of the normal joint structure, usually accompanied by shorting of the length of the phalanx. Gross osteolysis will be scored as "G" where applicable.

Erosion and JSN scores for each reader are calculated by taking the sum of the left and right joints as shown below.

$$\text{Erosion}_{\text{Reader}_i} = \text{Erosion}_{\text{Left}} + \text{Erosion}_{\text{Right}}$$

$$JSN_{\text{Reader}_i} = JSN_{\text{Left}} + JSN_{\text{Right}} \text{ for } i = 1, 2.$$

Thus, the maximum erosion score for all 40 joints in hands/wrists is 200. The maximum erosion score for all 12 joints in feet is 120. Thus, the total erosion score for hands/wrists and feet is 320 assessed on a total of 52 erosion joints.

The maximum score for JSN in all 40 hand/wrist joints is 160. The maximum score for JSN in all 12 feet joints is 48. Thus, the total JSN score for hand/wrist and feet is 208 based on total 52 JSN joints.

Since two independent readers evaluate each film, the mean score will be calculated for the two readers from the individual erosion and JSN scores as shown below:

$$\text{Erosion} = \frac{\text{Erosion}_{\text{Reader}1} + \text{Erosion}_{\text{Reader}2}}{2}$$

$$JSN = \frac{JSN_{\text{Reader}1} + JSN_{\text{Reader}2}}{2}$$

The mTSS for each reader is defined as the sum of the erosion and JSN scores:

$$TSS_{\text{Reader } i} = \text{Erosion}_{\text{Reader } i} + JSN_{\text{Reader } i} \text{ for } i = 1, 2.$$

The mTSS from Erosion score plus JSN score will be used for all x-ray endpoint calculations.

$$TSS = \text{Erosion} + JSN.$$

### **Handling of missing joints in mTSS score calculation**

For categorical score G and P, the maximum score per location should be assigned before any imputation.

Missing joint score imputation will be performed for Erosion and JSN respectively. If a score at a location/joint is missing then the methods described below will be used to calculate Erosion and JSN total score for that visit. However, if the missing score was present in a previous reading of the image (Study M16-002) then that previous reading's score will be used for missing score imputation.

#### **Method 1 (used in Study 1311.5):**

- If the scores of more than 50% of JSN scoring locations are available (e.g., 27 or more JSN scoring locations out of 52 total JSN scoring locations), the total JSN score would be calculated as Total JSN Score = Avg of all available scores\*52
- If 50% or less (e.g., 26 or fewer JSN scoring locations out of 52 total JSN scoring locations) of the JSN scoring locations are readable, the Total JSN Score will not be calculated
- If the scores of more than 50% of Erosion scoring locations are available (e.g., 27 or more Erosion scoring locations out of 52 total Erosion scoring locations), the total Erosion score would be calculated as Total Erosion Score = average of all available hand scores\*40 + average of all available foot scores\*12.
- If 50% or less (e.g., 26 or fewer erosion scoring locations out of 52 total erosion scoring locations) of the erosion scoring locations are readable, the Total erosion Score will not be calculated

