**Table 8. Summary of Efficacy Variables and Corresponding Analyses**

Efficacy Variables	Summary Method
Categorical Efficacy Endpoints:	
Secondary Binary Endpoint: ACR20 responses at all measured time points	
 
• Point estimates and 95% CIs of the response rates
 
• Imputation: OC
 

Other Categorical Endpoints: At all measured time points:	
 
• Point estimates and 95% CIs of the response rates
 
• Imputation: OC
 

 
• ACR50
 
• ACR70
 
• Minimal disease activity (MDA)
 
• PASI75 response in subjects with a <math>\geq 3\%</math> baseline PsO BSA
 
• PASI90 response in subjects with a <math>\geq 3\%</math> baseline PsO BSA
 
• PASI100 response in subjects with a <math>\geq 3\%</math> baseline PsO BSA
 
• sPGA clear and almost clear in subjects with a <math>\geq 3</math> baseline PsO BSA
 
• Psoriatic Arthritis Response Criteria (PsARC)
 
• European League Against Rheumatism (EULAR) Response
 
• Presence of dactylitis (yes/no)
 
• No Progression of mTSS
 
	
Continuous Efficacy Endpoints	
Secondary Continuous Endpoint: Change from baseline in Study 1311.5 at Week 24 (Study 1311.5), Week 24 (Study M16-244) and Week 48:	
 
• Point estimates, 95% CIs of mean change from baseline together with SD, Min, Q1, Median, Q3 and Max
 
• Imputation: OC
 

Change from baseline in Study M16-244 at all measured timepoints:	
 
• mTSS
 
• HAQ-DI
 
• SF-36
 

**Table 8.****Summary of Efficacy Variables and Corresponding Analyses  
(Continued)**

Other Continuous Endpoints:	
At all measure time points as compared to baseline in Study M16-244:	

• Point estimates, 95% CIs of mean change from baseline together with SD, Min, Q1, Median, Q3 and Max

• For SF-36, spyderdiagram will be provided

• Imputation: OC

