### 10.3 Secondary Efficacy Analyses

The following secondary endpoints will be summarized:

- ACR 20 response at all measured time points in Study M16-244
- Change in mTSS at Week 24 (Study 1311.5), Week 24 (Study M16-244), and Week 48 as compared to baseline in Study 1311.5
- Change in HAQ-DI at all measured time points in Study M16-244 compared to baseline in Study 1311.5
- Change SF-36 at all measured time points in Study M16-244 compared to baseline in Study 1311.5

For the change from baseline in continuous endpoints, the number of observations, mean, standard deviation, median, minimum, Q1, Q3 and maximum will be summarized. Point estimates and 95% CIs of mean change from baseline will be provided.

For the summary of binary endpoints by visit, point estimate and 95% CI will be calculated and presented.

The primary analysis for the above secondary efficacy endpoints will be performed based on the Safety Analysis Set with observed cases.

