### **No Progression**

No progression of mTSS is defined as a change in mTSS score less than or equal to 0.

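### mTSS Method 1 rescales each film on its own readable joints, so a joint lost at one visit creates a false change that can misclassify a subject under the zero cut-off for no progression

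*SAP*

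**What the plan says.** All the relevant rules are in SAP Section 10.7.20 unless noted.

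- **Level of imputation.** Where a joint score is missing, "then the methods described below will be used to calculate Erosion and JSN total score for that visit". Erosion and JSN are treated separately. A score from a previous reading of the same image, in a study labelled M16-002, is used first if there is one.
- **Method 1, erosion.** "the total Erosion score would be calculated as Total Erosion Score = average of all available hand scores" multiplied by 40, plus the average of the available foot scores multiplied by 12.
- **Method 1, JSN.** "the total JSN score would be calculated as Total JSN Score = Avg of all available scores" multiplied by 52.
- **Threshold.** Each rule applies when at least 27 of 52 locations are readable (for erosion: "If the scores of more than 50% of Erosion scoring locations are available"). Nothing requires the same locations to be readable at the visits being compared.
- **Immunology Convention Method.** A joint missing at baseline, or at every post-baseline visit, is dropped from all visits. Any other gap takes the joint's previous available score.
- **Cut-off.** "No progression of mTSS is defined as a change in mTSS score less than or equal to 0".
- **Endpoints.** SAP Section 10.3 lists as secondary "Change in mTSS at Week 24 (Study 1311.5), Week 24 (Study M16-244), and Week 48 as compared to baseline in Study 1311.5". SAP Table 8 lists "No Progression of mTSS" among the other categorical endpoints, with a 95% confidence interval on observed cases.

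The SAP does not say which of the two missing-joint methods feeds which endpoint.

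**The concern.** A change score should compare the same joints at two times. Method 1 compares two totals that may rest on different joints, each scaled up from its own average. Losing a joint that scores below the average raises that visit's total, and losing one above the average lowers it. The shift is usually a fraction of a point, but a cut-off at exactly 0 leaves no room for a fraction.

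What is at stake is the share of subjects reported as free of structural progression, which bears on the structural part of the secondary objective. The mean mTSS change gains some noise.

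**Working it through.** **Inputs.** From SAP Section 10.7.20: 40 hand/wrist and 12 foot locations; erosion scored 0–5 (hand) or 0–10 (foot); JSN scored 0–4; two readers averaged.

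**Plan's own figures.** Erosion 40×5 + 12×10 = 320; JSN 52×4 = 208; mTSS 320 + 208 = 528. These agree with the SAP ("the total erosion score for hands/wrists and feet is 320 assessed on a total of 52 erosion joints"). With every joint readable, Method 1 equals the plain sum.

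**False change in an unchanged subject.** Let S be the regional sum and s the score of one joint readable at baseline but not at follow-up.

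- Hand erosion: (S − s)×40/39 − S = (S − 40s)/39
- Foot erosion: (S − s)×12/11 − S = (S − 12s)/11
- JSN: (S − s)×52/51 − S = (S − 52s)/51

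The result is positive when s is below the regional mean, negative when above, and zero when equal. If the joint is lost at baseline instead, the sign reverses.

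| Region | S | s | Computed change |
|---|---|---|---|
| Hand erosion | 5 | 0 | +0.13 |
| Hand erosion | 10 | 0 | +0.26 |
| Hand erosion | 20 | 0 | +0.51 |
| Foot erosion | 5 | 0 | +0.45 |
| JSN | 10 | 0 | +0.20 |
| Hand erosion | 10 | 1 | −0.77 |
| Hand erosion | 10 | 2 | −1.79 |

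Every positive row turns an unchanged subject into a progressor. If only one of the two readers finds the joint unreadable, averaging halves the error (+0.13 for S = 10, s = 0), which still exceeds 0.

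**Hidden progression.**

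- True rise from 10 to 11, with a joint scored 2 unreadable at follow-up: (11 − 2)×40/39 = 9.23, a computed change of −0.77.
- True rise from 30 to 30.5, with a zero-score hand joint unreadable at baseline: 30.5 − 30×40/39 = −0.27.

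Both subjects are labelled as not progressing.

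**Same subject under the Immunology Convention Method.** S = 10, zero-score joint lost at follow-up: the baseline score of 0 is carried forward, so the total goes from 10 to 10 and the change is 0.

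**Frequency, given that a joint is lost.** This needs assumed joint-score distributions. With skewed scores, mean mTSS about 5 to 30, and one joint readable at only one of the two visits, simulations put 26% to 42% of unchanged subjects above 0. In a different set-up, with one location lost for both erosion and JSN and always at follow-up, the share was 63% to 89% (mean mTSS roughly 5 to 50). The mean false change was about 0 in both.

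**Effect on the no-progression rate.** Assume 10% of subjects have one such joint. With 26% to 39% of unchanged affected subjects misclassified, the loss before any offset runs from 0.10×0.26×0.60 = 1.6 points (60% unchanged) to 0.10×0.39×0.80 = 3.1 points (80% unchanged). After allowing for true progressors relabelled the other way, the simulated net falls were 1.6 to 2.1 points at 60% unchanged and 2.1 to 3.0 points at 80%.

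**The case against.** The strongest reply is that the SAP already holds a method without this fault. Method 1 is headed as the one used in Study 1311.5, so it can be read as kept for comparability, while the Immunology Convention text says its method will be used to derive mTSS. If that is the main method, the headline results are untouched. This stands as a limit on the consequence. It does not remove the point, because the SAP applies its methods in the plural, ranks neither, and says only that sensitivity analysis may be done as needed.

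A second reply is that previous readings fill gaps. That helps only where the same image was read before and the joint was scored then. The documents do not define M16-002 or show that the Week 24 and Week 48 films of this study have such a reading.

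A third is that the errors cancel. For the mean they do, nearly. A reader might infer that the secondary mean mTSS change is biased; the calculations do not support that, and its cost is variance. For a rate cut at 0 they do not cancel.

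A fourth is scale. The no-progression rate appears in SAP Table 8 but not among the secondary or further endpoints of the protocol or SAP Sections 10.3 and 10.4. The study is single-arm and descriptive, and its primary objective is safety. At an assumed rate of 70% and the protocol's maximum of 180 subjects, the 95% interval is already about ±7 points (1.96×√(0.7×0.3/180) = 0.067). That is fair and keeps the point modest.

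**Conclusion.** The point holds for Method 1 as written. A joint readable at only one of two visits gives a false change, and the zero cut-off lets that change decide whether a subject counts as progressing. The consequence is misclassification in the no-progression rate and added variance in the secondary mean change. It is confined to results where Method 1 is used and no earlier reading fills the gap. Subjects who score 0 throughout are unaffected.

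The number affected cannot be derived, because the documents give neither a rate of unreadable joints nor a score distribution. A fall of about 2 to 3 points rests on the assumed 10% of subjects with one such joint and 60% to 80% truly unchanged. A reader might infer a fall of 3 to 4 points by multiplying 10% by 28% to 41%. That treats every subject as unchanged and ignores progressors relabelled the other way, and nothing in the documents supports it. Nor is this an error in the score ranges, which reproduce. It is a missing-data rule that does not suit a change score.

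**What to change.** Use either of two routes, and state in the SAP which one feeds mTSS change and no progression.

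1. **Repair Method 1 where it feeds these endpoints.** For each comparison with baseline, compute each reader's two visit totals, including the adjudicator's, on the joints scored at both of those visits, prorated to 40 hand, 12 foot and 52 JSN locations. Apply the more-than-50% rule to that common set. Set the total to missing if a region has no common joint; the present formula is also undefined when all 12 foot locations are missing, although 40 of 52 pass the threshold. Then apply reader averaging and the adjudication rule to these totals. Working with visit totals rather than a per-reader change score matters because the adjudication rule selects among individual visit scores. An unchanged subject then has a change of exactly 0.
2. **Derive both endpoints from the Immunology Convention Method**, and keep Method 1 as defined only as a sensitivity analysis for comparability with Study 1311.5.

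The cost is SAP wording and limited programming, with no new data. Under the first route a few more films may fall below the 50% rule, and a subject's baseline total can differ slightly between the Week 24 and Week 48 comparisons. Under the second, carrying scores forward leans toward no progression, which the report should state.
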